Introduction. Malnutrition is recognized as a major concern by healthcare providers, as well as by patients, families, and caregivers. In a very recent survey, 28% of 1,035 patients, families and caregivers reported that malnutrition was a very significant problem, while 55% reported it was a somewhat significant problem in older adults 65 and older.²⁶ This response aligns with reports that up to 65% of older adults admitted to the hospital are malnourished (National Resource Center on Nutrition, Physical Activity, and Aging, 2015). Thus, it is essential to establish systematic malnutrition screening in the clinical setting and to develop intervention models and standards of nutritional care. The objective of this aim is to investigate the feasibility, fidelity and acceptability of a nutrition intervention protocol providing higher protein intakes before and after surgery in malnourished Veterans. To achieve the objective of this aim, we will test our working hypotheses that recruitment in clinic will have a high yield and that intervention fidelity (adherence, retention) and acceptability (attrition, patient satisfaction) will be predominantly satisfactory. The rationale for this aim is that successful completion of the proposed research will provide necessary knowledge to begin to identify feasible and acceptable interventions for community-dwelling Veterans who are preparing for surgical procedures. When the proposed studies for Aim 1.1 have been completed, it is our expectation that $\geq 75\%$ of patients approached for recruitment will agree to participate, $\geq 75\%$ of the time patients will adhere to the intervention, $\geq 80\%$ of the participants will remain in the study, and that $\geq 80\%$ of participants will find the intervention to be acceptable. Such findings would be of considerable importance, providing a patient-centered viewpoint that will inform the development of nutrition interventions that meet the standards and needs of high-risk Veteran Populations.

Specific Aim 1.2 – *To determine the effect size for planned future studies of enhanced protein supplementation in malnourished Veterans, with physical function as the primary outcome of interest. Of secondary interest are: biomarkers of inflammation (albumin, hsCRP, TNF- α , IL-6), dietary intake, hospital readmission, discharge location, length of skilled care, and ED admission, and physical activity.*

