Introduction. Older adults have reduced adaptive and regenerative capacities to recovery from a surgical insult.²⁷ Thus, when coupled with insufficient energy intake, malnutrition becomes the driver that leads to further deterioration of functional abilities, reduction in lean muscle mass, and inability to maintain physical reserve. A generous and balanced intake of high quality protein (~30 grams) is essential for achieving optimal protein synthesis in older adults²⁸ and is linked to lean mass retention.²⁹ The essential amino acids

found in complete (animal) proteins stimulate translation initiation of the mTOR signaling pathway and increase muscle protein synthesis in older individuals.²⁹ The objective of this aim is to research the effects of a meal-based protein enhanced perihabilitation intervention in malnourished older Veterans undergoing elective surgery on the primary outcome physical function and secondary outcomes, inflammatory biomarkers (albumin, hsCRP, TNF- α , IL-6), dietary intake, hospital readmission, discharge location, length of skilled care, and ED admission, and physical activity. To achieve the objective of this aim, we will test the working hypothesis that Veterans consuming the enhanced protein supplementation will have superior improvements in function compared to the control arm. Approach: We will further refine our working hypothesis in a two-armed pilot trial comparing a high protein nutrition supplement for two weeks pre and post-surgery to an education control arm. We will assess physical function (SPPB) and secondary outcomes two weeks before, the day of surgery, and four weeks post-surgery. The successful completion of the proposed research will provide preliminary data to test this hypothesis in a large scale randomized controlled trial. When the proposed studies for Aim 1.2 have been completed, it is our expectation that the protein intervention will prove to provide higher functional and physiological benefits relative to the control treatment, illustrating the importance of nutritional perihabilitation prior and following surgery in high-risk, vulnerable populations.

Design

[figure not shown]
This is a Randomized Controlled Study. Veterans will be enrolled until 84 participants have completed the study.

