Where i is an indicator of person, and time is defined as $t=1, 2$ (measuring week 2 or 6), and the β 's are regression coefficients connecting the predictors to the outcome. For brevity, we list β_4 as a vector of K regression coefficients linking the K covariates to the outcome. As defined, the overall test of the intervention effect will be the joint effect of group and group*time on 2 df (β_1 and β_2) assessing an overall effect of group, and if this group effect is constant over time. If significant, follow-up tests will assess where group differences lie. In particular, we note that if the time by group interaction is rejected, we will test if the groups differ at the end of 6 weeks (a test of effect at the completion of the intervention).

We will carefully examine model assumptions, including the distribution of model residuals, additively, linearity, and influential observations, and will, if necessary, re-parameterize the models or transform the outcomes accordingly.

We note that we have listed numerous measures to be analyzed as outcomes, but have listed only 2 domains of outcomes as primary (physical function and a biological index of nutrition status and inflammation). We will not adjust for Type-I error rate for these primary outcomes. Rather, we will warn the reader of the multiple outcomes tested and the chance for a Type-I error.

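### The Aim 1.2 Analysis Plan adds an undefined biological index as a second, unadjusted primary outcome, although Aim 1.2 itself makes physical function the only primary and the biomarkers secondary

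*Combined protocol and SAP*

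**What the plan says.** The sections of the combined protocol and SAP give different answers on what is primary for Aim 1.2.

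- **Statement of Specific Aim 1.2:** the effect size is to be determined "with physical function as the primary outcome of interest". The next sentence begins "Of secondary interest are: biomarkers of inflammation" and names albumin, hsCRP, TNF-alpha and IL-6.
- **Introduction to Specific Aim 1.2:** the hierarchy is repeated, with the effect to be studied "on the primary outcome physical function and secondary outcomes, inflammatory biomarkers". The instrument is also named: "We will assess physical function (SPPB) and secondary outcomes two weeks before, the day of surgery, and four weeks post-surgery".
- **Data Analysis and Statistical Considerations, Aim 1.2 Analysis Plan:** the authors "have listed only 2 domains of outcomes as primary (physical function and a biological index of nutrition status and inflammation"). They continue: "We will not adjust for Type-I error rate for these primary outcomes". In place of adjustment, readers are to be cautioned about the number of outcomes tested.
- **Secondary Outcomes:** the text refers to the primary outcome in the singular.
- **Power Estimate:** power is given for physical function only, with 40 per group, 80% power and two-tailed alpha of 0.05.
- **Measures and Data Collection Points table:** biological markers appear as one line. No index is listed.

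**The concern.** An analyst who follows the aims reports one primary result. An analyst who follows the Analysis Plan reports two. All of this is current text, and no other section settles the conflict.

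The second primary is also not specified. No section says which markers enter the index, how they are weighted, or which direction counts as benefit. An outcome in that state can be assembled after the data are examined and still carry the primary label. A general caution about multiple testing does not deal with this, because the reader cannot tell how many constructions were possible. The introduction to Aim 1.2 states a directional working hypothesis for function, so it matters which result is the primary one and at what error rate it is tested.

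**Working it through.** **1. The plan's own figure.** Inputs from the Power Estimate: changes of 23.7 and -21.3 m, SD of change 67.75, n = 40 per group, 80% power, two-sided alpha 0.05.

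- Literature effect: (23.7 - (-21.3)) / 67.75 = 45.0 / 67.75 = 0.664. The plan gives 0.66.
- Detectable standardized difference, normal approximation: (1.960 + 0.842) × √(2/40) = 0.626.
- Detectable standardized difference, two-sample t test with 78 df: 0.6343. The plan's 0.634 is reproduced, and power at 0.634 is 79.96%.

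This figure holds for one outcome tested at the full 0.05. It therefore fits the single primary in the aims. Its inputs are six-minute-walk distances, so it supports one powered domain (physical function) rather than SPPB in particular.

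**2. False-positive chance with two primaries.** Assume each is tested at 0.05 and either may count as a positive result.

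- One primary: 5%.
- Two independent tests: 1 - 0.95² = 0.0975, or 9.75%.
- Correlated tests (bivariate normal statistics; the documents give no correlations, so these are assumed):

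| Correlation | At least one false-positive primary |
|---|---|
| 0 | 9.75% |
| 0.3 | 9.5% |
| 0.5 | 9.1% |
| 0.7 | 8.3% |
| 0.9 | 7.0% |

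The correlated rows use one-degree-of-freedom statistics. The plan's overall test has 2 df, so they are illustrative. The 9.75% needs only independence and a 0.05 level for each test.

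**3. If the index were instead tested marker by marker.** SPPB plus four markers makes five tests: 1 - 0.95⁵ = 0.226, or 22.6% if independent, and about 18% at a common correlation of 0.5. This needs an assumption that the text does not make.

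**4. What each resolution does to the power statement.**

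| Option | n per arm | Alpha per primary | Detectable difference (t test) | Power at 0.634 |
|---|---|---|---|---|
| Physical function only | 40 | 0.05 | 0.634 | 80.0% |
| Two primaries, Bonferroni | 40 | 0.025 | 0.701 | 70.8% |
| Two primaries, Bonferroni | 42 | 0.025 | 0.683 | 73.2% |

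With two adjusted primaries the detectable difference exceeds the literature effect of 0.664, and 80% power at 0.634 would need 49 per arm. The present sample size agrees with the aims and would not support an either/or rule with error control.

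**The case against.** The best defence is that this is a pilot. Its purpose is feasibility, fidelity and acceptability, and Aim 1.2 is there to obtain an effect size. The SPPB estimate and its confidence interval are the same whatever label the index carries. The plan states openly that it will not adjust and promises a caution to readers, which is a defensible choice in a pilot. All of that stands, and it lowers the severity. It does not say which outcome is primary, and it does not define the index.

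A reader might also infer more than the documents support:

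- **That the index means four tests (22.6%), or six-way testing with handgrip added (1 - 0.95⁶ = 26.5%).** The Analysis Plan speaks of one index, in the singular. The introduction to Aim 1.2 ties physical function to SPPB, and no section places handgrip in the primary domain. The word domains leaves some room but does not establish either count.
- **That the index consists of the same markers that the aims call secondary.** This is likely, since they are the only biological markers named, but the components are never listed.
- **That the trial succeeds if either primary is positive.** No success rule is stated, so the 9.75% is conditional on that reading.
- **That the singular primary outcome in the Secondary Outcomes paragraph proves the point.** It may be generic wording, and little weight should rest on it.

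**Conclusion.** The contradiction is real. The aims and the Power Estimate treat physical function as the one primary domain, while the Analysis Plan adds a biological index that is defined nowhere and tests both without adjustment. The firm defect is the inconsistent hierarchy together with the undefined index. Non-adjustment in itself is not the error.

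The size is modest and conditional. If either primary may count as positive, the false-positive chance rises from 5% to at most 9.75% for two tests, and less under positive correlation. That bound assumes the index is fixed in advance and tested once; choosing its form after seeing the data is not covered by it. The documents do not support the larger figures as a description of the plan. Rating: should fix.

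**What to change.** In the Aim 1.2 Analysis Plan:

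1. Replace the sentence on two primary domains with a statement that physical function measured by SPPB is the single primary outcome of Aim 1.2, tested by the joint test and the six-week follow-up test already described there.
2. State that albumin, hsCRP, TNF-alpha and IL-6 are secondary and will be reported individually with estimates and confidence intervals. The composite need not be deleted. If it is kept, make it a secondary outcome whose components, weights and direction are written down before any data are examined.
3. Reword the two Type-I error sentences together, because the second depends on the first. The caution about multiple testing should then apply to the secondary outcomes.

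The cost is wording only: no new data, and the 0.634 at 40 per group stands. The downside is that a biomarker result can no longer be called a primary finding, a status the aims do not give it.

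If the sponsor does intend two primaries, the alternative is to define the index, amend the aims, and state whether either or both must be met. An either/or rule needs alpha control, and the power section must match whichever rule is chosen.

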Setting: The POSH Clinic is an interdisciplinary collaboration between surgery, anesthesiology, geriatrics, nursing, and physical therapy to provide perioperative surgical care for high-risk Veterans at the Durham VAMC. The clinic opens with a conference to review patients to be seen that day. The surgery chief resident presents and the team covers technical issues with the surgery and selection of anesthesia, as well as covering a list of specific care points. The POSH clinic estimates 200 – 400 patients enrolled annually.

VAPOSH Veterans who are malnourished or at risk of being malnourished will be randomly assigned on a 1:1 ratio by computer-generated random numbers to either an education (nutritional counseling) control (PoshControl) arm or high-protein perihabilitation (PeriHab) arm. All will receive nutrition education. Participants in the PeriHab arm will also be provided with high quality protein supplements that will bring their protein intakes to at least 30 grams for each of the 3 meals per day.

Study Arms:

- PoshControl; n = 42: During their VAPOSH clinic visit, participants will be provided nutrition counseling and prescribed to consume protein at 1.0 g/kg of body weight in the form of educational handouts explained by a Registered Dietitian. Participants will also be instructed to consume 1 oral nutrition supplement per day two weeks before surgery.
- PeriHab; n = 42: PeriHab will be provided nutrition counseling and prescribed to consume protein at 1.6 g/kg of body weight) as well as provided 30 g of high quality protein to some 3 times per day for 2 weeks before and 4 weeks after surgery.

Measurements:

After the participant has been consented and HIPAA Authorization forms have been signed, a Registered Dietitian will administer the NRS-2002 screening tool, the PG-SGA, and nutrition focused physical exam. A patient screening “nourished” on the NRS-2002, PG-SGA, and nutrition focused physical exam will not be included in the study. For study candidates who are malnourished or at nutritional risk we will then proceed with baseline assessments (described below). Upon the completion of all baseline assessments, the participant will be randomized to PeriHab or PoshControl. The following variables will be blocked in this order: 1) surgery type and 2) American Society of Anesthesiology (ASA) Physical Status Classification System (≥ 3 versus < 3). An equal number of participants will be randomized across the two arms.

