Measures and Data Collection Points

| Measure | When Collected |
|------------------------------------|-----------------------|
| NSR-2002 | Baseline (T1), T2, T3 |
| PG-SGA | T1, T2, T3 |
| Nutrition Focused Physical Exam | T1, T2, T3 |
| Cognition | T1 |
| Medical History | T1 |
| Demographic | T1 |
| Anthropometrics | T1, T2, T3 |
| Comorbidity Status | T1 |
| Bristol Stool Chart | T1 |
| Short Physical Performance Battery | T1, T2, T3 |
| Handgrip strength | T1, T2, T3 |
| Biological Markers | T1, T2, T3 |
| Postoperative outcomes | T3 |

| | |
|---|----------------------------|
| Physical Activity | T1, T2, T3 |
| PROMIS and PROMIS GLOBAL QUESTIONNAIRES | T1, T2, T3 |
| Three-day Food Record | T1, T2, T3 |
| Protein Checklist | Daily |
| 24-Hour Dietary Recall | Weekly between time points |
| Participant Satisfaction Questionnaire | T3 |
| Participant Acceptability | T3 |

Risk/Benefit Assessment

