Secondary Outcomes: At the conclusion of the study, we will have a rich database with which to conduct follow-up exploratory analyses. We will perform multiple exploratory analyses of the remaining measures. In addition to the impact of the intervention on the secondary outcomes, we will assess mediation of the group effect on the primary outcome by demographic, comorbid and adherence variables. Subjects may differ in their process of change depending on baseline demographic and functional status values. Second, we will assess the functional form of the change over time, by looking at non-linear functions of change. For example, change in function and performance is likely to be non-linear, initially changing quickly and leveling off at points distal from baseline. It would be important to note if this change differed by group. Finally, we will assess whether the trajectories of change, irrespective of group assignment, are similar for individuals. In this application, we have listed several variables, which we expect to change as a result of the intervention. We further hypothesize that all these variables will change in the same pattern. To test this hypothesis, across the

range of outcome measures, we can look at overall change through the use of multivariate tests (Bock⁴⁴ or Anderson⁴⁵) for the singly measured functional items, and by assessment of correlated trajectories for those outcomes measured repeatedly. With appropriate weighting for number of observations per individuals, the correlation between individual trajectories can be assessed. A positive correlation between the trajectories for any two outcomes will indicate that the subjects changed similarly for the 2 outcomes, and will provide additional support for the notion that the intervention had a generalized effect across the outcomes.

Significant correlations would perhaps indicate mechanistic/causal linkage between variables over time, or, from a reliability standpoint, may indicate that the subsequent trial may want to employ summary measures aggregating across outcome measures, or, alternatively, employ multivariate tests across several outcomes to assess the group differences, reducing the chance of Type-I error inherent in the testing of multiple variables.

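### The plan names mediation by demographic and comorbidity variables, which are fixed before randomisation; its stated reason is effect modification, for which no model term is given

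*Combined protocol and SAP*

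**What the plan says.** Secondary Outcomes, within Data Analysis and Statistical Considerations, announces that "we will assess mediation of the group effect on the primary outcome by demographic, comorbid and adherence variables". The sentence after it reads: "Subjects may differ in their process of change depending on baseline demographic and functional status values". The section as a whole is exploratory: "We will perform multiple exploratory analyses of the remaining measures".

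The table of Measures and Data Collection Points gives the timing of the variables: "Demographic | T1" and "Comorbidity Status | T1". Neither is listed again at T2 or T3. Postoperative outcomes have their own row, at T3. The Measurements text puts allocation after these assessments: "Upon the completion of all baseline assessments, the participant will be randomized to PeriHab or PoshControl". Under Setting, participants are "randomly assigned on a 1:1 ratio by computer-generated random numbers".

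The Aim 1.2 Analysis Plan models each outcome on group, time, group-by-time and covariates. The covariates enter as "a vector of K regression coefficients linking the K covariates to the outcome", that is, as main effects. Age, race and number of comorbidities are its examples of covariates to be chosen in advance.

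**The concern.** A mediator is a variable that treatment changes and that in turn changes the outcome. A variable recorded once, before allocation, cannot be changed by treatment. For demographics and comorbidity the analysis named in the plan therefore has no effect to estimate. The following sentence asks whether the response differs by baseline status. That is a moderation question, and it needs a group-by-variable interaction, which neither the Aim 1.2 model nor any other section specifies.

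The plan also treats the same kinds of variable as adjustment covariates in the primary models. If they were mediators, adjusting for them would remove part of the treatment effect, so the two roles conflict.

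What is at stake is modest but practical. The pilot is meant to shape a larger trial, and the section expects these analyses to throw light on causal pathways. An analyst who follows the text literally would fit a model that cannot show who responds, although the data to look at that question will have been collected.

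**Working it through.** **The plan's own figure.** The documents give no figure for this analysis. The one figure used here as a yardstick is the detectable standardised difference of 0.634 in Power Estimate (40 per group, 80% power, two-sided alpha 0.05). A two-sample t calculation gives 0.6343, so it reproduces. The normal approximation gives (1.960 + 0.842) × √(2/40) = 0.626.

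**Step 1: can these variables mediate?** Write the indirect effect as a × b, where a is the effect of group on the variable and b is the effect of the variable on the outcome given group. The variables are measured at T1 and allocation comes afterwards, at random. The expected value of a is therefore zero, and so is the expected indirect effect, whatever b is.

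**Step 2: how large is the chance component?** Take a baseline variable in SD units and 42 per arm (Study Arms).

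- SE of the group difference at baseline = √(2/42) = 0.218.
- SD of the indirect effect ≈ 0.218 × b.
- The documents do not give b. I assume 0.1 to 0.5 SD: 0.218 × 0.1 = 0.022, and 0.218 × 0.5 = 0.109.

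This assumes simple randomisation. The plan blocks on surgery type and ASA class (≥3 versus <3), which would shrink the figure for comorbidity variables related to ASA class.

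**Step 3: what would a literal mediation test do?** In 20,000 simulated trials of 40 per arm, a product-of-coefficients (Sobel) test was compared with a group-by-variable interaction test. The assumptions, none from the documents, are a binary factor at 50% prevalence, a prognostic effect of 0.5 SD in the control arm, and an average group effect of 0.634 SD.

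| True interaction (SD) | Mean indirect effect | Mediation test rejects | Interaction test rejects |
|---|---|---|---|
| 0 | -0.0006 | 0.6% | 5.0% |
| 0.634 | 0.0001 | 1.9% | 28% |
| 1.27 | 0.0002 | 3.1% | 79% |

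The indirect effect averages zero in every row. The mediation test stays almost blind even when moderation is strong.

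**Step 4: what could the interaction analysis achieve?** For a binary factor with prevalence p and 40 per arm, SE of the interaction = √(2 × [1/(40p) + 1/(40(1−p))]) in outcome SD units. The difference detectable at 80% power is 2.802 × SE.

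| Split (assumed) | SE | Detectable interaction (SD) | Power for 0.634 SD |
|---|---|---|---|
| 50/50 | 0.447 | 1.25 | 29% |
| 80/20 | 0.559 | 1.57 | 21% |
| 90/10 | 0.745 | 2.09 | 14% |

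This treats the outcome as a single change score. The repeated-measures model may do somewhat better, but the documents give no correlations from which to say by how much.

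**Step 5: adherence.** This is the third kind of variable in the sentence. It arises after randomisation, so it could mediate. The fidelity part of the analysis plan (headed Aim 2.1) defines a container proportion that is not limited to one arm, and controls also return lids and a check-off sheet at T2. Against that, controls have their own measure, a count of dietary changes. The supplement targets differ too: one a day before surgery for controls, three a day before and after surgery for PeriHab. The measures are only partly comparable between arms.

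**The case against.** The strongest reply is that mediation is a slip for moderation. The next sentence makes the intent fairly clear, and the plan names no indirect effect, path model or other mediation method. The Aim 1.2 equation is offered as a general form, so the missing interaction term may only mean that the exploratory models were not written out. This is probably right about intent. It does not remove the point: the analysis named and the reason given for it conflict, and no section states the model that would fit the reason.

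A reader might go further and infer that the trial will report chance imbalance as mechanism. The documents do not support that. Under the simulation assumptions a literal mediation test rejected in only 0.6% to 3.1% of trials, so the usual result would be nothing found. The plan also has sensitivity analyses for the influence of group imbalance on the treatment estimate.

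A reader might also express the chance indirect effect as a share of 0.634. That does not work either. The size depends on an undocumented prognostic effect, and 0.634 is a detectable difference justified from six-minute-walk data, not an expected effect on the SPPB. Nor do the documents show that adherence is unusable as a mediator, since the container proportion can be computed in both arms before surgery.

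Finally, the replacement is itself weak at this sample size. That stands, and it is why only estimation is proposed.

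**Conclusion.** The point holds for demographic and comorbidity variables. They are fixed before allocation, cannot lie on the path from treatment to physical function, and are attached to a moderation question that has no specified model. This follows from the timing in the documents and needs no numerical assumption. The chance indirect effect (SD about 0.02 to 0.11) and the interaction power (about 14% to 29%) rest on assumed prognostic strength and factor prevalence, and should be read as ranges.

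The matter is minor. The analysis is labelled exploratory, and the primary test, the power statement and the feasibility aims are untouched. It would be too strong to say that the trial cannot examine who benefits: the plan raises that question and collects the data for it. What is missing is the correct term and the model.

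**What to change.** For demographic, comorbidity and baseline-function variables, replace mediation with moderation. Extend the Aim 1.2 model for each chosen variable V by V, V × time, group × V and group × V × time. Name the variables in advance. Report the interaction estimates with confidence intervals, label them exploratory, and state that power is low.

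Keep mediation for post-randomisation variables measured the same way in both arms. Protein intake from the weekly 24-hour recalls is one candidate, because the recalls are made in both arms between time points. If adherence is kept as a mediator, state one definition that applies to both arms and the period it covers. Say also that a mediation estimate assumes no unmeasured confounding of mediator and outcome, since the mediator is not randomised.

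The cost is a change of wording and a different exploratory model. No new data, visits or participants are needed. The drawback is that the interaction estimates will be imprecise.

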The results of these analyses will provide invaluable information regarding the process and functional forms and, potentially, the causal pathways of the intervention process. For example, one important analysis will enter 'level of compliance to the intervention' into the analysis, allowing for a 'per protocol' analysis of the results.

Power Estimate: Estimate effect sizes for the physical function between-group comparisons and the power available to detect effect with two-tailed tests are provided below for the total N= 80. The objective of this pilot study is to perform preliminary evaluation of a nutrition perihabilitation program in malnourished Veterans, in preparation for a larger grant submission. This pilot work will allow us to conduct sample size, effect sizes, and power analyses for a larger clinical trial. To date, no randomized controlled nutrition perihabilitation study has been conducted in malnourished Veterans. As such, we turned to the literature. Gillis et al.,⁴⁶ reported that older adults undergoing colorectal resectioning surgery who were given nutrition supplementation 3 weeks before surgery improved by 23.7 meters on the 6 minute walk test while the arm given nutrition supplement following the surgery declined by -21.3 meters. The pooled standard deviation of these changes was 67.75. Thus, a standard difference of $0.66 = (23.7 - (-21.3))/67.75$ was observed. Differences of this magnitude have been labeled as 'medium' in the statistical power literature (70). Assuming a standard deviation in the change scores of 67.75, n=40 per group, power=80% and alpha=0.05 (two-tailed), we are powered to detect a difference in changes scores of a standardized magnitude of 0.634, in line with the results of Gillis et al.⁴⁶

References

2. Morley J. Decreased food intake with aging. *J Gerontol Med Sci* 2001;56:81-88.

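### A correlation between outcome trajectories that ignores treatment arm cannot support a generalised intervention effect, yet Secondary Outcomes says a positive one will.

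*Combined protocol and SAP*

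**What the plan says.** The relevant text is in the combined protocol and SAP, Data Analysis and Statistical Considerations, under Secondary Outcomes. The section is introduced as exploratory: "we will have a rich database with which to conduct follow-up exploratory analyses". Its last listed analysis is described as follows: "we will assess whether the trajectories of change, irrespective of group assignment, are similar for individuals". For outcomes measured repeatedly, the method is a correlation: "With appropriate weighting for number of observations per individuals, the correlation between individual trajectories can be assessed".

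The interpretation is then fixed in advance. "A positive correlation between the trajectories for any two outcomes will indicate that the subjects changed similarly for the 2 outcomes", and this, the sentence continues, "will provide additional support for the notion that the intervention had a generalized effect across the outcomes". No arm adjustment, null value, threshold or rule on scoring direction is attached.

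The following paragraph is more guarded. It says that significant correlations might point to linked mechanisms, or might suggest summary measures or multivariate tests for the later trial. The intervention effect itself is tested elsewhere, under Aim 1.2 Analysis Plan, by a joint 2-df test of group and group-by-time.

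**The concern.** Evidence for an intervention effect has to come from a contrast between the randomised arms, and this statistic contains none. All patients undergo surgery and are followed from two weeks before it to four weeks after. Someone who recovers well may gain on SPPB, handgrip and physical activity together in either arm, and someone with a complication may lose on all three. Those shared differences between patients produce a positive correlation whether or not the supplement does anything.

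The stakes are moderate. No primary test depends on the sentence. But Power Estimate describes the pilot as preparation for a larger grant application, and a statement that the intervention acted broadly could be written into the report on evidence that does not bear on it.

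**Working it through.** **Inputs from the documents.** Power Estimate uses a total of 80 (40 per arm): "the power available to detect effect with two-tailed tests are provided below for the total N= 80". Design gives a slightly larger number: "Veterans will be enrolled until 84 participants have completed the study". Patients "will be randomly assigned on a 1:1 ratio by computer-generated random numbers". The detectable standardised difference is stated as 0.634, for 80% power and two-sided alpha 0.05.

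**The plan's own figures.** The literature difference is (23.7 + 21.3)/67.75 = 0.664, against the stated 0.66. A two-sample t-test with 40 per arm (noncentral t, 78 df) has 80% power at 0.6343, against the stated 0.634. Both reproduce. The documents give no figure for the trajectory correlation. The value 0.634 serves below only as a convenient size for a real effect.

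**Assumed input.** Rho is the within-arm correlation, across patients, between change on one outcome and change on another. The documents do not give it, so a range is shown.

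**Expected pooled correlation.** With 1:1 allocation, unit within-arm SDs and an effect d on both outcomes, pooling the arms adds d²/4 to the covariance and to each variance:

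r = (rho + d²/4) / (1 + d²/4)

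For d = 0.634, d²/4 = 0.402/4 = 0.1005.

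- rho = 0.30: (0.30 + 0.1005)/1.1005 = 0.364.
- rho = 0: 0.1005/1.1005 = 0.091.

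**How often the criterion is met.** 20,000 simulated trials per setting, N = 80, bivariate normal change scores, arms pooled. One change score per outcome is a simplification of the three-visit trajectories.

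| rho (assumed) | r > 0, no effect | r > 0 and two-sided p < 0.05, no effect | r > 0, effect 0.634 on both | mean r, effect on both |
|---|---|---|---|---|
| -0.3 | 0.4% | 0.0% | 5.4% | -0.18 |
| -0.1 | 19% | 0.2% | 50% | 0.00 |
| 0 | 50% | 2.3% | 80% | 0.09 |
| 0.1 | 81% | 15% | 95% | 0.18 |
| 0.2 | 96% | 44% | 99.4% | 0.27 |
| 0.3 | 99.7% | 78% | 99.97% | 0.36 |

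With N = 84 the no-effect figures for r > 0 are almost the same: 97% at rho = 0.2 and 99.8% at 0.3.

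**Analytic check.** P(r > 0) is approximately Φ(√(N − 3) × atanh(rho)). For N = 80 and rho = 0.2 this is Φ(8.775 × 0.2027) = Φ(1.78) = 96%. Inverting, P(r > 0) with no effect reaches 95% at rho of about 0.19 and 99% at about 0.26.

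**Opposite directions.** Suppose benefit raises SPPB by d and lowers hsCRP by d, with neither reverse-scored. The expected correlation is then (rho − d²/4)/(1 + d²/4), which at rho = 0 is −0.091. By symmetry with the table, r > 0 occurs in 100% − 80% = 20% of trials, against 50% with no effect. A real general benefit would make the stated support less likely.

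**The case against.** The strongest reply is that this is one sentence in an exploratory section. It offers additional support for a notion, on top of a separate group test, and nothing in the plan lets the correlation override that test. This stands. A reader might infer that the plan would announce an intervention effect regardless of the truth, and the documents do not support that.

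A reader might also infer that the positive correlation appears almost always when there is no effect. That holds only if rho is about 0.2 or more. Such values are plausible for pairs such as SPPB and handgrip, but the documents do not state them. At rho = 0 the figure is 50%, and at negative rho it is lower. When rho is near zero the sign does respond somewhat to a real effect (50% to 80%). Since rho is unknown, an observed positive correlation still cannot be attributed to treatment.

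It could be argued that the phrase setting arm aside governs only the opening sentence of that analysis. But the correlation sentences that follow do not bring arm back in. Nor would adjusting for arm rescue the inference: a constant treatment effect shifts arm means and leaves the within-arm correlation unchanged.

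Finally, a reader might take a multivariate test of group to be planned already. Secondary Outcomes names multivariate tests of overall change for singly measured items in this trial. It mentions multivariate tests of group differences only as something the later trial might use.

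**Conclusion.** The point holds as a flaw of interpretation that should be corrected. That the statistic contains no treatment contrast follows from the text and needs no assumed value. How often it would mislead depends on rho: for a given pair with no effect and N = 80, about 50% of trials at rho = 0, 81% at 0.1, 96% at 0.2 and over 99% at 0.3, but 19% at −0.1. These figures assume normal change scores. The weak response to treatment (0.30 to 0.36) assumes an effect of 0.634 SD on both outcomes. The sign can mislead either way when outcomes are not aligned in direction. The damage is limited to one exploratory claim, and the 2-df group test is untouched.

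**What to change.** Three changes under Secondary Outcomes:

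1. Delete the clause that reads a positive correlation as support for an intervention effect.
2. Report the trajectory correlations within arm, or adjusted for arm, as description only. Use them to judge whether outcomes could be combined in the next trial, which the section already has in mind.
3. Base any generalised-effect statement on between-arm comparisons. These can be the group tests already planned for each outcome, or an added multivariate or joint-model test of group with all outcomes scored so that higher means better.

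The first two are changes of wording, plus the specification of arm in one calculation. The added test in the third is a small new analysis that needs a sentence or two of specification. It uses data already to be collected, so no visits, measurements or patients are added.
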